##### **9.3.2.2. Other Comparisons of Interest**

The analysis described above will also be performed using the PP population and the results will be compared for consistency with the results from the ITT-E population.

### 9.3.2.3. Secondary comparisons

The following key secondary comparison will be tested:

- Treatment with CAB LA + RPV LA will be declared non-inferior to current ART if the lower end of a two-sided 95% confidence interval for the difference between the two groups in response rates at Week 48 lies above -10%.
- Superiority of CAB LA + RPV LA compared to continuation of current ART with respect to change from baseline HIVTSQs total score at Week 44;
- Changes in the PIN acceptance score within the CAB LA + RPV LA arm from Day 4 to Week 48

### 9.3.2.4. Planned Analyses

At least two analyses will be conducted to evaluate primary and secondary objectives of the protocol, one after all subjects have completed their visits at Week 48 and one after Week 96. Further data cuts and analyses may be conducted as necessary after Week 96 in order to support regulatory submissions and publications. The Week 48 analysis will be primary. No adjustment for multiplicity caused by repeated evaluation of the primary endpoint will be made as the Week 96 analyses will be secondary.

An IDMC will be instituted to ensure external objective medical and/or statistical review of efficacy and safety in order to protect the ethical interests and well-being of subjects and to protect the scientific validity of this study (201585) and study 201584. An ad-hoc review of data by the IDMC will be triggered whenever the number of confirmed virologic failures (Section 5.5.4) in the CAB LA + RPV LA exceeds thresholds pre-specified in the IDMC charter. Further, an interim futility analysis will be performed for the IDMC to evaluate the efficacy and safety of CAB LA + RPV LA when approximately 50% of subjects have completed their visit at Week 24; the sponsor will remain blinded to this analysis. Full details of the methods, timing, decision criteria and operating characteristics will be pre-specified in the IDMC Charter.

Since the statistical stopping guidelines will not result in early stopping for positive efficacy findings, these planned analyses will not inflate the type I error rate for the primary treatment comparison at Week 48.

## 9.4. Key Elements of Analysis Plan

The study design is open-label. However, the central GSK team responsible for the conduct and analysis of the study will not review any summaries of data grouped by treatment prior to database freeze for the primary Week 48 analysis.

This study is conducted in parallel with study 201584 (FLAIR) with the aim to pool data generated from the current study with study 201584, in order to evaluate key program objectives.

### 9.4.1. Primary Analyses

For the primary efficacy analysis, each participant's response (e.g., virologic failure) will be calculated according to the FDA's Snapshot algorithm. The primary analysis at Week 48 will take place after the last participant has had their Week 48 viral load assessed, including a retest if required. This algorithm treats all participants without HIV RNA data at the visit of interest (due to missing data or discontinuation of study drug prior to visit window) as non-responders, as well as subjects who switch their concomitant ART prior to the visit of interest since no switches are allowed in this protocol. Otherwise, virologic success or failure will be determined by the last available HIV-1 RNA assessment while the participant is on-treatment within the window of the visit of interest. Full details on the Snapshot algorithm will be contained in the RAP.

The primary analysis will be based on the ITT-E population using the Snapshot dataset. The primary comparison will be made at a one-sided 2.5% level of significance. Treatment with CAB LA + RPV LA will be declared non-inferior to current ART if the upper end of a two-sided 95% confidence interval for the difference between the two groups (CAB – current ART) in virologic failure rates at Week 48 lies below 6%.

For the primary comparison, adjusted estimates of the difference in the rate of failures between the two arms will be presented along with CIs based on a stratified analysis using Cochran-Mantel Haenszel (CMH) weights. All CIs will be two-sided and the analysis will be stratified according to the baseline third agent class (INI, NNRTI, or PI) and gender at birth. If the adjusted treatment difference is not estimable due to overly sparse stratification and/or low number of subjects with virologic failure, then the primary comparison will be adjusted for baseline third agent class only; if this also encounters numerical issues then the primary comparison will be based on the unadjusted analysis.

The CMH estimate of the common difference in rates across strata will be calculated as the weighted average of the strata-specific estimates of the difference in response rates between the two arms as follows:

- If  $n_k$  is the number of CAB treated participants,  $m_k$  is the number of current ART control arm treated participants, and  $N_k = n_k + m_k$  is the total number of participants in the  $k$ th stratum, then the CMH estimate is given by

$$\hat{d}_{cmh} = \frac{\sum W_k \hat{d}_k}{\sum W_k}$$

where

$$W_k = \frac{n_k m_k}{N_k}$$

are CMH weights and  $\hat{d}_k$  are estimates of the differences in response rates between the two treatment arms,  $f_{1a}-f_{1c}$ , for the  $k$ th stratum.

using the variance estimator  $\hat{\text{var}}(\hat{d}_{cmh})$ , given by [Sato, 1989], which is consistent in both sparse data and large strata. The full equation for this variance estimate will be provided in the RAP.

The weighted least squares chi-squared statistic [Fleiss, 1981] will be used to test for one-way homogeneity across the levels of each categorical variable, with each categorical variable considered separately. Following Lui and Kelly [Lui, 2000],  $\frac{1}{2}$  will be added to each cell in any strata for which the stratum-specific rate estimates of either  $f_{1a}$  or  $f_{1c}$  are zero or one, and tests will be one-sided. Any heterogeneity found to be statistically significant will be explored and if necessary results will be reported for each level of the categorical variable. Investigation of heterogeneity will be confined to the primary endpoint using the Week 48 Snapshot analysis. Tests of homogeneity will be assessed at the one-sided 10% level of significance. Full details will be contained in the RAP.

On-treatment data collected from extra visits within a window will be included in the derivation of the Snapshot response/failure but summary tables using observed case (OC) datasets will only use the data captured closest to the target visit date. Detailed explanations of the derivation of visit windows will be included in the RAP. Any changes to the original analysis plan in the protocol will be described in the RAP and/or clinical study report (CSR).

The analysis described above will also be performed using the PP population and the results will be compared for consistency with the results from the ITT-E population.

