## **Analysis**

The primary analysis at Week 48 will take place after the last participant has had their Week 48 viral load assessed, including a retest if required. The primary analysis method for the proportion of participants defined as Snapshot virologic failures at Week 48 will be a Cochran-Mantel Haenszel test stratified by randomization stratification factors. A non-inferiority margin of 6% will be used for this comparison, where if the upper limit of the 95% confidence interval (CI) of the difference in failure rate between the two study arms is less than 6%, non-inferiority will be demonstrated.

Assuming the true virologic failure rate is 3% for the CAB LA + RPV LA injectable regimen and 2% for the current ART arm, this would provide approximately 97% to

show non-inferiority at a 2.5% one-sided significance level. If we observe a 2% failure rate for the current ART arm, then non-inferiority would be declared if we observe a 5% or lower failure rate for the CAB LA + RPV LA arm (i.e. an observed treatment difference less than 3 percentage points for [CAB LA + RPV LA] – current ART).

A key secondary analysis will evaluate the proportion of responders (HIV-1 RNA <50 c/mL per Snapshot) at Week 48 using a Cochran-Mantel Haenszel test stratified by randomization stratification factors. A non-inferiority margin of -10% will be used for this secondary comparison, where if the lower limit of the 95% confidence interval (CI) of the difference in responder rate between the two study arms is greater than -10%, non-inferiority will be demonstrated. Assuming true response rates for the CAB LA + RPV LA arm and current ART arm are both 87%, the sample size of 285 per arm will provide at least 94% power to show non-inferiority at a 2.5% one-sided significance level.

In addition, the data from this study, together with data from a separate study, 201584, will be combined to assess non-inferiority using a 4% non-inferiority margin. The combined sample size from both studies (570 pooled per arm) will provide 90% power, under the assumptions described above, to show non-inferiority for the proportion of participants with virologic failure (per FDA's snapshot algorithm for assessing HIV-1 RNA  $\geq$  50 c/mL) at Week 48.

201585 (ATLAS) is being conducted in parallel with study 201584 (FLAIR) with the aim to pool data generated from the current study with study 201584, in order to evaluate key program objectives.

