## 9. STATISTICAL CONSIDERATIONS AND DATA ANALYSES

### 9.1. Hypotheses

The study is designed to demonstrate that the antiviral effect of switching to CAB LA + RPV LA (CAB) is non-inferior to continuation of current first line antiretroviral regimen (current ART) at Week 48 in HIV-1 infected ART-experienced participants. Non-inferiority in the proportion of participants with virologic failure at Week 48 (per FDA's snapshot algorithm for assessing HIV-1 RNA  $\geq 50$  copies/mL) can be concluded if the upper bound of a two-sided 95% confidence interval for the difference in failure rates between the two treatment arms (CAB – current ART) is not more than 6%.

If  $f_{la}$  is the failure rate for CAB LA + RPV LA and  $f_c$  is the failure rate for current ART then the hypotheses can be written as follows:

$$H_0: f_{la} - f_c \geq 6\% \quad H_1: f_{la} - f_c < 6\%$$

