### 9.2. Sample Size Considerations

#### 9.2.1. Sample Size Assumptions

This study will randomize approximately 285 participants per arm. Assuming the true virologic failure rate is 3% for the CAB LA + RPV LA injectable regimen and 2% for current ART arm, a non-inferiority margin of 6%, and a 2.5% one-sided significance level, this would provide approximately 97% power to show non-inferiority for the proportion of participants with virologic failure (per FDA's snapshot algorithm for assessing HIV-1 RNA  $\geq 50$  copies/mL) at Week 48.

This sample size of 285 participants per arm will also provide at least 90% power to show non-inferiority in the proportion of participants with plasma HIV-1 RNA  $< 50$  c/mL (per FDA's snapshot algorithm) at Week 48 over a range of true response rates, on the basis of a -10% non-inferiority margin and 2.5% one-sided significance level (see [Table 13](#)). Assuming true response rates for the CAB LA + RPV LA arm and current ART arm are both 87%, the power is at least 94% to show non-inferiority for this key secondary endpoint.

In addition, the data from this study, together with data from a separate study, 201584 (FLAIR), will be combined to assess non-inferiority using a 4% non-inferiority margin. The combined sample size from both studies (570 pooled per arm) will provide 90% power, under the assumptions described above, to show non-inferiority for the proportion of participants with virologic failure (per FDA's snapshot algorithm for assessing HIV-1 RNA  $\geq 50$  c/mL) at Week 48.

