**Figure 8 Sensitivity of Estimated Power for Snapshot Virologic Failure**

Table 12 shows the power with 285 randomized per arm and the sample size required to guarantee 90% power, for a range of ‘true’ virologic failure rates. For instance, even if the failure rates were 3% for CAB LA + RPV LA and 1% for the control arm, the study will still have over 92% power to meet its primary objective with the planned sample size. However, if the failure rates were 4% for CAB LA + RPV LA and 2% for control, an additional ninety-six participants per arm would be required to obtain 90% power for the primary treatment comparison.

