#### **9.3.2. Treatment Comparisons**

##### **9.3.2.1. Primary Comparison of Interest**

The primary analysis will be based on the ITT-E population using the Snapshot dataset. The primary comparison will be made at a one-sided 2.5% level of significance. Treatment with CAB LA + RPV LA will be declared non-inferior to current ART if the upper end of a two-sided 95% confidence interval for the difference between the two groups (CAB – current ART) in virologic failure rates at Week 48 lies below 6%.

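### The planned primary confidence interval has a true one-sided error of about 3.2–3.9% at the 6% margin, not the stated 2.5%, at the 1–3% control failure rates the protocol expects

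*Protocol*

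**What the plan says.** Section 9.3.2.1 fixes the level: "The primary comparison will be made at a one-sided 2.5% level of significance". Section 9.4.1 repeats it and gives the rule: non-inferiority is declared if the upper end of the two-sided 95% interval for the difference "in virologic failure rates at Week 48 lies below 6" percent. The null in section 9.1 is an excess of 6 points or more.

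Section 9.4.1 also fixes how the interval is built: stratum differences combined with CMH weights over third-agent class and gender at birth, with the Sato variance, described as one "which is consistent in both sparse data and large strata". Only the full variance equation is left to the RAP. Fewer or no strata are used only if the adjusted difference cannot be estimated or meets numerical problems.

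On size, section 9.2.1 states: "This study will randomize approximately 285 participants per arm". Its power statement begins: "Assuming the true virologic failure rate is 3% for the CAB LA + RPV LA injectable regimen and 2% for current ART arm", and arrives at about 97%. Section 9.2.2 adds that at 3% versus 1% "the study will still have over 92% power to meet its primary objective with the planned sample size". Section 9.2.1.1 gives 1 to 3% as the typical range of observed failure rates.

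**The concern.** An interval built from an estimate and its standard error is reliable when the estimate is close to normal. Here few failures are expected. At the boundary with 2% control failure, the expected counts are 285 × 0.02 = 5.7 control and 285 × 0.08 = 22.8 injectable-arm failures. When the injectable arm has few failures by chance, its estimated variance is small as well, so the upper limit falls too low exactly when the estimate is most favourable. Consistency of the variance estimator is a large-sample property and does not secure the 2.5% tail at these counts.

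The primary decision rule is at stake. Section 9.2.1.1 treats an increase beyond 4 to 6 percent as clinically unjustifiable, so 6% is already the outer limit, and the chance of crossing it wrongly should be the chance stated.

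**Working it through.** **Inputs (protocol).** n = 285 per arm, margin 6%, one-sided 2.5% (z = 1.96), design rates 3% versus 2%, control range 1–3%, six strata (three classes × two genders).

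**1. Reproduce the stated power.**
- Formula: power = Φ((0.06 − δ)/SE − 1.96), with SE = √[(p₁(1−p₁) + p₀(1−p₀))/285].
- 3% versus 2%: SE = √[(0.0291 + 0.0196)/285] = 0.01307. Then 0.05/0.01307 = 3.825 and Φ(1.865) = 96.9% (Table 12: 96.8%).
- 3% versus 1%: SE = √[(0.0291 + 0.0099)/285] = 0.01170. Then 0.04/0.01170 = 3.419 and Φ(1.459) = 92.8% (Table 12: 92.7%).
- Nine numeric rows of Table 12 reproduce within 0.1 point, so the stated powers rest on the normal approximation with unpooled variance.

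**2. Actual error at the boundary.** Set the injectable rate to the control rate plus 6 points. Sum the product of the two binomial probabilities over every pair of counts for which the upper limit is below 6%. With one stratum and equal arms, the Sato variance and the unpooled variance reject on the same pairs.

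| Control rate | Estimate + 1.96 SE, exact | Six-stratum CMH/Sato, simulated | Miettinen-Nurminen score, exact |
|---|---|---|---|
| 1% | 3.93% | 3.9–4.0% | 2.13% |
| 2% | 3.52% | 3.4–3.5% | 2.16% |
| 3% | 3.23% | 3.1–3.2% | 2.21% |

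The simulations used 2,000,000 replicates per setting, with balanced and slightly imbalanced strata, equal and unequal control rates, and three sets of class shares. The protocol gives about 40% INI and about 25% women. The NNRTI/PI split is an assumption, and the result barely depends on it. The excess is present with a single stratum, so it does not come from sparse strata and the fallback to fewer strata would not remove it.

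**3. What this means in counts.** Take 6/285 control failures (2.1%).
- 14/285 (4.9%): difference 0.0281, SE 0.01537, upper limit 0.0281 + 1.96 × 0.01537 = 5.82%, which passes. The score limit is 6.22%, which does not.
- 13 failures is the most that passes under the score limit.
- For each control count from 2 to 9, the planned interval admits one more injectable-arm failure than the score limit.

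**4. Exact power by the same enumeration.**

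| Rates | Stated | Planned interval | Score interval |
|---|---|---|---|
| 3% vs 2% | about 97% | 95.5% | 92.0% |
| 3% vs 1% | over 92% | 89.1% | 80.6% |

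**5. Pooled analysis, only if it uses the same approach** (570 per arm, 4% margin, 3% versus 2%). Exact power is 89.0% with the planned interval and 84.9% with the score interval, against the stated 90%. Error at 2% control failure is 3.1% and 2.3%.

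**The case against.** The strongest reply is that the excess is small. It is 0.7 to 1.4 percentage points, or one event at the threshold. In margin terms, the planned rule has 2.5% error at true excesses of 6.34, 6.28 and 6.22 points for control failure of 1%, 2% and 3%, a shift of 0.2 to 0.3 point in a margin set by clinical judgement. A level attached to an asymptotic interval is commonly understood as nominal, and the score interval errs slightly the other way. This stands, and it lowers the severity. It does not make the stated level correct.

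A second reply is that the protocol never uses the words normal approximation and leaves the Sato equation to the RAP. The reading is an inference, but nothing in the text points to a score or exact limit, and Table 12 reproduces under it. The choice of variance formula matters little: a stratified unpooled variance gives 3.3–4.1%.

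Three stronger readings are tempting and are not supported:
- **That the consistency statement is false.** It is true of the variance estimator. The fault is pairing this interval with a 2.5% level.
- **That the synopsis illustration gives a wrong decision.** It says "then non-inferiority would be declared if we observe a 5% or lower failure rate for the CAB LA + RPV LA arm" when control failure is 2%. Exactly 5% versus 2% gives 0.03 + 1.96 × √[(0.0475 + 0.0196)/285] = 6.007%. But that is 14.25 versus 5.7 events, which cannot occur, and the nearest attainable result, 14 versus 6, passes. The synopsis's own parenthesis (difference below 3 points) and section 9.2.1.1 (below 5%) give the right rule. This is an editorial mismatch.
- **That the pooled analysis has the same fault.** This protocol does not fix the pooled interval, so those figures are conditional.

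**Conclusion.** The point holds. The interval fixed in section 9.4.1, read as estimate plus 1.96 standard errors, does not deliver the one-sided 2.5% level in section 9.3.2.1. True error at the 6% boundary is about 3.9%, 3.5% and 3.2% at control failure of 1%, 2% and 3%. The stated powers are 1 to 4 points too high for that interval.

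This rests on 285 per arm, the standard published form of the Sato variance, and control failure in the protocol's own range. It does not show that the trial is underpowered at its design assumption: exact power at 3% versus 2% exceeds 90% with either interval. It is a should-fix, because the excess is modest but falls on the primary decision rule.

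**What to change.** - **Section 9.4.1.** Take the primary two-sided 95% interval from a stratified Miettinen-Nurminen score interval with the same strata and CMH weights. Keep the CMH/Sato interval as supportive.
- **Synopsis and sections 4.1, 9.2.1 and 9.2.2, including Table 12.** Restate power exactly for the interval adopted. With the score interval this is about 92% at 3% versus 2% and about 81% at 3% versus 1%. If the planned interval is kept, it is 95.5% and 89.1%, and the actual error should be stated.
- **Pooled analysis.** Name its interval. If it follows the same approach, replace 90% power with 89.0% (planned interval) or about 85% (score interval).
- **Editorial.** Align the synopsis wording of 5% or lower with the below-5% rule in section 9.2.1.1, or with the new threshold if the score interval is adopted.

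The change is to wording and calculations, to be made before the Week 48 analysis, with no extra participants or data. The cost is lower stated power, most visibly in the 3% versus 1% scenario, where the protocol's reassurance of over 92% would no longer stand.

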#### **9.4.2. Secondary Analyses**

A key secondary analysis will evaluate the proportion of responders (HIV-1 RNA <50 c/mL per Snapshot) at Week 48 using a Cochran-Mantel Haenszel test stratified by baseline third agent class (INI, NNRTI, or PI) and gender at birth. A non-inferiority margin of -10% will be used for this secondary comparison, where if the lower limit of the 95% confidence interval (CI) of the difference in responder rate between the two study arms is greater than -10%, non-inferiority will be demonstrated.

Proportion of participants with plasma HIV-1 RNA <200 c/mL and <50 c/mL and confirmed virologic failure, respectively, for the ITT-E population over time will be summarized using the Snapshot algorithm. Proportion of participants with confirmed virologic failures will also be summarized over time.

Absolute values and change from Baseline in plasma HIV-1 RNA and CD4+ lymphocyte count will be summarized over time.

The incidence of HIV-1 disease progression (AIDS and death) will be presented.

An efficacy analysis at Week 48 will also be presented by baseline third agent class.

The OC dataset will be the primary dataset used for analysis of safety endpoints.

Statistical analysis of selected biomarkers and fasting lipids may be performed overall and by baseline third agent class using appropriate methods for missing data. Further details will be detailed in the RAP.

The proportion of participants reporting AEs will be tabulated for each treatment group. The following summaries of AEs will be provided:

- Incidence and severity of all AEs
- Incidence and severity of treatment related AEs
- Incidence and severity of AEs leading to withdrawal
- Incidence of SAEs

The incidence and severity of treatment related AEs, SAEs and AEs leading to withdrawal will also be assessed by baseline third agent class.

Changes from baseline in laboratory (including fasting lipids) and vital signs data will be summarized by visit and treatment group. In addition, the number and percentage of participants with graded laboratory toxicities (based on DAIDS categories) will be summarized by treatment group. The number and percentage of participants with graded laboratory toxicities and the change from baseline in fasting lipids will also be assessed by baseline third agent class.

Change from baseline in renal, bone and cardiovascular biomarkers will be summarized by treatment and visit.

Further details of safety and exploratory analyses will be included in the RAP.

